Study Title:

Efficacy of Multimodal Periarticular Injections in Operatively Treated Ankle Fractures: A Randomized Controlled Trial

Date: 8/8/2016

NCT: NCT02967172

Study Protocol:

Periarticular fractures (bone breaks extending into the joint surface) treated by orthopaedic surgeons are associated with significant pain in the post-operative period, often requiring high doses of opioid analgesics. In recent years, the high risk of misuse, abuse, and death associated with prescription opioid use has become increasingly evident. Although physicians are being advised to avoid administration of opioid prescriptions, alternative pain management options are limited. Currently, there is a need to investigate different pain management models in order to provide safe and effective pain relief during the post-operative period.

We aim to evaluate the effectiveness of peri-incisional multimodal injections as an alternative post-operative pain control method in orthopaedic trauma patients with operative ankle fractures. Approximately 200 patients will be randomized to either receive or not receive intra-operative injections in addition to standard opioid analgesic regimens. Post-operative pain management outcomes will be assessed and compared between the 2 study groups to determine effectiveness of the injections.

The proposed study will build upon related work to advance post-operative pain control regimens in orthopaedic surgery. Goals include the reduction of unnecessary patient suffering, reliance on opioids, and length of stay, while improving patient experience. These aims will be accomplished through the expansion of currently used multimodal periarticular injections from populations undergoing elective surgery to orthopaedic trauma patients with rotational ankle fractures.

The study design is a prospective, double-blinded, randomized controlled trial. Patients included in the study will be randomly assigned to one of two treatment groups: intra-operative multimodal periarticular injection or control (no injection). The peri-incisional injection will consist of ropivacaine, epinephrine, and morphine. All pharmacologic agents in the anesthetic cocktail are FDA approved and have been previously used in combination during other types of orthopaedic surgeries.

All patients included in the study will receive standard post-operative opioid analgesic regimens, administered ‘per needed’, regardless of their assigned treatment group per study protocol. ≥ 40 patients will be randomly assigned to each group. The patients enrolled in the investigation as well as health care professionals performing post-operative assessments and collecting data will be blinded to treatment allocation.

The feasibility of multimodal peri-incisional injections is supported by their current efficacy in populations undergoing elective orthopedic surgeries. These injections may be equally effective at reducing pain compared to regional anesthesia with continuous infusions, and single-shot nerve blocks.[7, 8]

We hypothesize that the injection cohort will have reduced pain scores, lower narcotic requirements, shorter length of stay, and be more likely to discharge to home following surgery.

We aim to evaluate the effectiveness of peri-incisional multimodal injections as an alternative post-operative pain control method in orthopaedic trauma patients with operative, closed, rotational ankle fractures. Patients undergoing surgical internal fixation of such fractures will be randomized to either receive or not receive intra-operative injections in addition to standard opioid analgesic regimens.

Control group will receive no injection and will receive IV and oral analgesics post-operatively.

Treatment group will receive injection during surgery into the periarticular space of ropivacaine, morphine, and epinephrine. They will also be provided with IV and oral analgesics post-operatively.

We will evaluate effectiveness of intra-operative injections by assessing inter-group differences in post-operative pain management outcomes, including: (1) subjective patient pain levels via visual analog scales in the immediate postoperative period; (2) quantity of opioid analgesics required prior to discharge; (3) post-operative length of stay; (4) discharge status (e.g. SNF, Rehab, Home).

We hypothesize that the injection cohort will have reduced pain scores, lower narcotic requirements, shorter length of stay, and be more likely to discharge to home following surgery.

Following consent, patients will be randomized by the research team using Microsoft Word (R) Random Number Generator.

Patients will be blinded as to whether they received the injection or not. This is possible as they will be unconscious in surgery during their procedure. While an inpatient, the patients will be notified that they may ask which arm of the study they are in during their 3 month followup visit***. Until then they will stay blinded.

They will then be treated with internal fixation of their fracture(s) as per standard of care.

During this surgery, patients randomized to the peri-incisional injection cohort will receive a single, 25 mL intra-operative injection with medication following completion of fracture fixation and just prior to skin closure. The injection will be administered as such:

20 mL injected into the peri-incisional soft tissues in a circumferential fashion.

5mL injected into the ankle joint.

This will take approximately 2 minutes of total surgery time.

Following surgery, patients in the treatment and non-treatment groups will both be provided with the same intravenous (patient-controlled analgesia) and oral pain medications scheduled "per needed".

Following surgery, (and again at their followup visits up to 3 months following surgery) the research team will examine the patient medical record and record narcotic use by the patient during their hospital stay. They will also record clinical outcomes from the medical record. (Notably VAS score). At 3 months the patient will no longer be followed in the study. At this point, the patients requesting information on which treatment arm they were in can be told.

No follow-up after 3 months.

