Study Title:

Efficacy of Multimodal Periarticular Injections in Operatively Treated Ankle Fractures: A Randomized Controlled Trial

Date: 8/8/2016

NCT: NCT02967172

Statistical Analysis Plan:

We will compare the two groups by improvement in the following measures:

Visual Analog Scores scores recorded as Standard of Care during daily rounds
Patient controlled analgesia usage as recorded as Standard of Care in Medical Record
Time spent in hospital
Standard of care outcome measures noted in Patient Medical Record

Standard statistical analysis will be performed to analyze differences between groups. ANOVA, T-Test, and Kolmogorov-Smirnov, and other tests will be used.

Based on a power analysis we estimate a minimal sample size of forty patients in each group to detect a 1.5 point difference in the Visual Analog Score (VAS) at each recording, with a standard deviation of 2.0 points, a p-value of .05, and a power of 80% or higher. Additional subjects (total subjects = 200) will aid in subgroup analyses, and ensure that we maintain an adequate sample size even if we run into issues with patient compliance (e.g. refusal of VAS during post-op stay) or unintentional de-blinding (nurse, student, resident etc. accidentally telling patient their treatment assignment) following the procedure.

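### The SAP's PCA-only opioid measure leaves out the morphine in the study injection and the oral medication, so it can show lower PCA demand but not lower total opioid use

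*Protocol*

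**What the plan says.** The Protocol describes the study injection in its design paragraph: "The peri-incisional injection will consist of ropivacaine, epinephrine, and morphine". Patients assigned to it "will receive a single, 25 mL intra-operative injection with medication following completion of fracture fixation and just prior to skin closure". For the comparator: "Control group will receive no injection and will receive IV and oral analgesics post-operatively". Morphine as part of the study intervention therefore goes to one arm only.

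The opioid outcome is worded in three ways:

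- The Protocol's outcome list covers "inter-group differences in post-operative pain management outcomes", and its second item is "quantity of opioid analgesics required prior to discharge".
- The Protocol's closing paragraphs on data collection say that the team will examine the medical record and "record narcotic use by the patient during their hospital stay".
- The SAP's list of measures has "Patient controlled analgesia usage as recorded as Standard of Care in Medical Record".

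Both arms receive PCA and oral pain medication as needed. The Protocol hypothesises a lower narcotic requirement in the injection arm and names less reliance on opioids among its goals. On blinding, it says that "health care professionals performing post-operative assessments and collecting data will be blinded to treatment allocation".

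**The concern.** The intervention contains a drug of the class whose use is an outcome. Whether that drug counts towards the outcome decides what the result means, and neither document settles it.

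PCA use could fall for three reasons: the local anaesthetic reduces pain, the injected morphine acts locally, or the injected morphine takes the place of opioid that the patient would otherwise have self-administered. In the third case only the route has changed. PCA usage alone cannot separate these. It also misses any shift between PCA and oral medication, although both arms receive both.

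At stake is how far the opioid result can be taken. The trial is motivated by the harms of prescription opioids, and readers will be inclined to take a fall in PCA use as a fall in opioid use overall. The SAP's measure does not support that step.

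**Working it through.** **1. The plan's own figure.** The SAP's only power statement concerns VAS: difference 1.5, SD 2.0, p-value .05, power 80% or higher, forty per group. With a two-sided test (assumed), n = 2 × (1.96 + 0.8416)² / (1.5/2.0)² = 2 × 7.849 / 0.5625 = 27.9, so 28 per arm. Forty per arm gives Φ(0.75 × √(40/2) − 1.96) = Φ(1.39) ≈ 92%. Forty thus meets the 80%-or-higher condition without being the minimum at 80%. This does not bear on the present point, except that no comparable figure exists for opioid use.

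**2. What each wording counts.**

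| Wording | Injected morphine | Oral opioid |
|---|---|---|
| SAP: PCA usage | excluded by construction | excluded |
| Protocol outcome list: opioids required before discharge, under post-operative outcomes | probably excluded; no start time given | included |
| Protocol data collection: narcotic use during the stay | could be included; not stated | included |

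Neither document says whether the injected morphine is counted or how different opioids are put on one scale. Blinded data collectors could not enter the injected dose without learning the allocation.

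**3. What leaving it out does.** Let m be the injected morphine, in the same units as post-operative use. Let D be the control mean minus the injection mean of post-operative opioid use. The difference in total opioid is then D − m. If D = m, the totals are equal, yet the post-operative comparison still shows a difference of m.

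**4. Illustration.** Inputs from the documents: a minimum of 40 per arm, and 200 in total, which is 100 per arm if allocation is 1:1 (ratio not stated). Assumed: r = m/SD, where SD is that of post-operative opioid use; full replacement; no other effect of the injection; a two-sided 5% comparison of means. The chance of a significant result is

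P = Φ(r × √(n/2) − 1.96)

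| r | 40 per arm | 100 per arm |
|---|---|---|
| 0.1 | Φ(0.447 − 1.96) = 7% | Φ(0.707 − 1.96) = 11% |
| 0.25 | Φ(1.118 − 1.96) = 20% | Φ(1.768 − 1.96) = 42% |
| 0.5 | Φ(2.236 − 1.96) = 61% | Φ(3.536 − 1.96) = 94% |

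Substitution alone reaches 80% at r = (1.96 + 0.8416) × √(2/n), which is 0.63 with 40 per arm and 0.40 with 100 per arm. Once m is added to the injection arm, the expected difference in these scenarios is zero and the rejection rate returns to the nominal 5%.

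**5. Partial replacement.** If only a fraction f is replaced, r in the formula becomes f × m/SD. Half replacement of an amount equal to 0.5 SD falls on the 0.25 row.

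**The case against.** The strongest reply is that post-operative requirement is a proper outcome. The whole injection, morphine included, is the randomised intervention, and later demand is its effect. If patients ask for less afterwards, their post-operative requirement really is lower. The Protocol hypothesises about requirements and speaks of reliance, not total exposure. This stands. A reader might infer that a fall in PCA use would be a false finding or a biased comparison. The documents do not support that: the comparison is valid for PCA demand, and the difficulty lies in reading it as total opioid.

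A reader might also infer that the plan has decided to count only what is taken after surgery. That is certain for the SAP's measure and the natural reading of the Protocol's outcome list. The data-collection wording, however, is broad enough to take in an intra-operative dose. The outcome is undefined across the two documents rather than expressly restricted. The SAP's general item on other standard-of-care measures might admit more opioid data, but it names none.

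The percentages are open to a fair objection as well. The morphine amount, the SD and the degree of replacement are all assumed. The PCA drug is not named, and nothing in the documents equates a soft-tissue and joint injection with intravenous use. The illustration also gives the local anaesthetic no effect. The figures show what could happen, and at 0.1 SD the problem is small.

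Finally, VAS drives the sample size, and opioid use is one of four listed outcomes. That limits how serious the point is. It does not remove it, since a lower narcotic requirement is an explicit hypothesis.

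**Conclusion.** The point holds in a limited form. Only the injection arm receives morphine as part of the study treatment, the SAP's sole named opioid measure cannot contain it and also drops oral medication, and nothing in either document adds it back. The planned analysis can support a statement about post-operative PCA demand. It cannot support one about total opioid use.

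The size is unknown, because it depends on an amount and an SD that the documents do not give. Under full replacement, the chance of a significant difference with equal totals runs from 7% to 61% with 40 per arm and from 11% to 94% with 100 per arm, for an injected amount between 0.1 and 0.5 SD. It would not be right to conclude that any observed reduction must be substitution; the documents permit that explanation but do not establish it. This is an inexpensive improvement to what the trial can conclude about opioids, and it does not invalidate the design.

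**What to change.** Replace the SAP's PCA-only measure with one definition used in both documents: all post-operative opioids, PCA and oral, up to discharge, in morphine equivalents by a stated conversion, and labelled as post-operative requirement. State explicitly that the injected morphine is not part of this measure.

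Add a pre-specified supportive analysis of total opioid from surgery to discharge, with the injected morphine included in the injection arm. The injected amount should be added at the analysis stage or by an unblinded person, so that data collectors stay blinded.

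Tie each claim to its own analysis: lower post-operative requirement to the first, lower total opioid use to the second. Neither claim need depend on the other.

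The cost is one more derived variable, one more analysis and a controlled step for adding the injected amount. If that amount is the same for every treated patient, the step only adds a constant to that arm. The downside for the sponsor is that the total-opioid result may look less favourable. Nothing in the treatment of patients changes.

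### The in-hospital opioid quantity cannot separate lower opioid need from earlier discharge if stay differs by arm, so it does not by itself support lower narcotic requirements

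*Protocol*

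**What the plan says.** The protocol's outcome list names "2) quantity of opioid analgesics required prior to discharge; (3) post-operative length of stay", with discharge status as the fourth outcome. Its data-collection text says that the research team will "record narcotic use by the patient during their hospital stay". The record is opened again at follow-up visits up to 3 months, but the narcotic item stays limited to the hospital stay. IV PCA and oral drugs are the same in both arms and are given as needed.

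The hypothesis predicts, for the injection arm, "reduced pain scores, lower narcotic requirements, shorter length of stay, and be more likely to discharge to home following surgery".

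The SAP's list of measures has "Patient controlled analgesia usage as recorded as Standard of Care in Medical Record" and, as a separate item, "Time spent in hospital". On method it says only that "ANOVA, T-Test, and Kolmogorov-Smirnov, and other tests will be used".

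Neither document gives a fixed post-operative window for opioid use, a per-time rate, an adjustment for stay, or a rule for patients who leave early. The word total does not appear. A cumulative amount is the natural reading of a quantity collected over the stay with no rate.

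**The concern.** As-needed opioid can keep adding up for as long as the patient is in hospital. If the injection arm leaves sooner, as the protocol predicts, its patients are counted over a shorter period. Their quantity can then be smaller even if their need at any given hour after surgery is the same. Use after discharge is not recorded, so a shift from hospital to home would not be seen.

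At stake is the wording of the conclusion. The protocol is motivated by opioid harm and lists less reliance on opioids among its goals. A lower quantity to discharge would be reported as support for lower narcotic requirements, although the same result could arise from earlier discharge.

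**Working it through.** **The plan's only computed figure.** The SAP gives 40 per group for a 1.5-point VAS difference, SD 2.0, alpha .05 and power of 80% or higher. Two-sided, n = 2(1.960 + 0.842)² × (2.0/1.5)² = 27.9, so 28 per group. At 40 per group, power = Φ(1.5/(2.0√(2/40)) − 1.960) = Φ(1.394) = 92%. So 40 is more than the minimum for 80% but satisfies the SAP's wording. The figure concerns VAS. Nothing in either document sizes the opioid comparison.

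**Inputs for the opioid check (all assumed; the documents give none).** Stay L is gamma with CV 0.5 (shape 4), mean 2.5 days in control and 2.0 with injection. The patient's opioid rate r is gamma with CV 0.5 and mean 40 units/day in both arms, independent of L, so need is equal. The unit cancels from all the results. Sample sizes are 40 per arm (the stated minimum) and 100 per arm (half of 200). The test is a Welch t-test at two-sided .05.

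**Constant use.** The total is T = rL.
- Means: 40 × 2.5 = 100 and 40 × 2.0 = 80, so 20% lower.
- CV² of T = 1.25 × 1.25 − 1 = 0.5625, so CV = 0.75 and the SDs are 75 and 60.
- 40 per arm: SE = √((75² + 60²)/40) = 15.2; 20/15.2 = 1.32; chance of p<.05 ≈ Φ(1.32 − 1.96) = 26%.
- 100 per arm: SE = 9.6; 20/9.6 = 2.08; Φ(0.12) = 55%.

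**Declining use at exp(−d per day).** The total is T = r(1 − e^(−dL))/d, with mean 40 × (1 − (1 + d × mean/4)^(−4))/d.
- d = 0.5: 40 × 1.326 = 53.0 v 40 × 1.181 = 47.2, so 11% lower.
- d = 1: 40 × 0.857 = 34.3 v 40 × 0.802 = 32.1, so 6% lower.

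Simulation (10,000 trials per setting) agrees with the constant-use arithmetic and gives the rest:

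| Use over time | Total, injection v control | p<.05, 40 per arm | p<.05, 100 per arm |
|---|---|---|---|
| Constant | 20% lower | 26% | 55% |
| exp(−0.5/day) | 11% lower | 14% | 28% |
| exp(−1/day) | 6% lower | 8% | 13 to 14% |
| Any, equal stay | no difference | about 5% | about 5% |

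**Fixed 24 h window in the same model.** The arm difference falls to 1 to 2% and p<.05 occurs in 5 to 6% of trials. With a mean stay of 1.75 days in the injection arm it occurs in at most 7 to 8%. The small excess comes from patients who leave before 24 h: 8% at a mean stay of 2.5 days, 14% at 2.0 and 20% at 1.75.

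**Use per inpatient day.** With no drug effect and d = 0.5, mean use per day is about 9% higher in the arm with the 20% shorter stay, because the low-use later days drop out. Dividing by stay replaces one distortion with another in the opposite direction.

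**The case against.** The strongest reply is that stay is itself an outcome of randomised treatment. Patients and post-operative assessors are blinded, so the likeliest route from an analgesic injection to a shorter stay is better pain control. In-hospital opioid quantity is then a legitimate effect of treatment. This stands: the comparison is valid for inpatient consumption, and the rates above are not false-positive rates for that quantity. They mislead only when read as need.

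A reader might infer that the opioid comparison is biased and the result void. The documents do not support that. Without a difference in stay there is no distortion, and a difference is so far only the protocol's hypothesis. Nor do waits for a SNF or rehab bed that are unrelated to treatment bias the comparison; randomisation balances them and they add noise.

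The SAP measure also weakens the link. It is PCA usage, and if PCA ends before discharge (the documents do not say), it has an early window of its own. Capping accrual at one day in the same model leaves about 2% lower use and 5 to 6% rejection. But the SAP states no such window, and PCA usage is narrower than the protocol's opioid outcome.

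Finally, stay is reported alongside, so a reader could see that it differed. That would flag the problem without resolving it.

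**Conclusion.** The point holds in a limited form. As written, a lower opioid quantity to discharge shows lower inpatient consumption. If stay differs by arm, it does not show lower need. The direction follows from the documents: collection bounded only by discharge, as-needed dosing, a predicted shorter stay, and no window or adjustment.

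The size does not follow from the documents. It depends on the assumed 20% difference in stay and on how fast use declines. The range shown runs from a 6% to a 20% lower total, and from 8% to 55% of trials reaching p<.05. The constant-use figures are the upper end of that range and should not be quoted alone.

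It is a should-fix. VAS is the only powered outcome, and its comparison does not use the opioid quantity. It would be going too far to say that the trial cannot meet its purpose: opioid use is one of four outcomes, and the stated goals also cover suffering, length of stay and patient experience.

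**What to change.** Pre-specify, in both documents, the main opioid comparison as total opioid, IV plus oral, over a fixed window from the end of surgery that is common to both arms and short enough that nearly all patients are still in hospital (for example the first 24 h). State the rule for patients discharged before it ends. This also reconciles the protocol's opioid outcome with the SAP's PCA usage.

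Keep the total to discharge as a secondary measure of inpatient consumption, interpreted beside length of stay. Report use per inpatient day as descriptive only. Discharge prescriptions, if extracted, are not consumption and cannot stand in for use at home.

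The cost is outcome wording in two documents. The source is the medical record already under review, provided that it gives the time of each dose. Randomisation, treatment and sample size do not change. The small downside is that use after the window leaves the main opioid comparison. The window should be fixed before any data are seen, since one chosen afterwards would not be credible.

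### Patients are randomised after consent although the arms do not differ until just before skin closure, and nothing described keeps care in between independent of the arm

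*Protocol*

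**What the plan says.** The Protocol's text is unnumbered, but its order is clear.

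- **Randomisation:** "Following consent, patients will be randomized by the research team using Microsoft Word (R) Random Number Generator".
- **Surgery, described after randomisation and patient blinding:** "They will then be treated with internal fixation of their fracture(s) as per standard of care".
- **Injection, for the treatment arm only:** "intra-operative injection with medication following completion of fracture fixation and just prior to skin closure". Controls receive no injection, and no placebo is mentioned.
- **Blinding of patients:** "This is possible as they will be unconscious in surgery during their procedure".
- **Blinding of staff:** "health care professionals performing post-operative assessments and collecting data will be blinded to treatment allocation". Surgeons, anaesthesia staff and other theatre staff are not listed.
- **Equal care across arms, after surgery only:** both groups "will both be provided with the same intravenous (patient-controlled analgesia) and oral pain medications".

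Neither document describes concealment of the assignment. Neither standardises, or plans to record, the anaesthetic, any regional block or intra-operative opioid. Neither defines an analysis set. The reasons the SAP gives for enrolling 200 are subgroup analyses, refusal of VAS during the post-operative stay, and de-blinding after the procedure. Loss between randomisation and surgery is not mentioned.

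**The concern.** Randomisation balances what precedes it. Anything that happens afterwards is balanced only if it does not depend on the arm. Here the anaesthetic, any intra-operative analgesia and the fixation itself all fall between assignment and the first moment at which the arms are meant to differ.

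Pain in the immediate post-operative period and opioid use before discharge are outcomes that such care could alter. If theatre staff knew that a patient was a control and gave more analgesia, the contrast would shrink. If the injection arm received more, the contrast would be exaggerated. Because this care comes after randomisation, it could not safely be adjusted for as a baseline variable.

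In addition, a patient who is randomised and then has no operation has no post-operative outcome, yet counts as randomised. Both problems can be avoided, because the arm is not needed until closure.

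**Working it through.** **Step 1. Sequence and protection.** The following is set out from the Protocol.

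| Stage | Does described care differ by arm? | Protection stated |
|---|---|---|
| Consent | No | Not needed |
| Randomisation by research team | No | No concealment described |
| Anaesthesia and fixation | No | Patient unconscious; no staff blinding or equal-care rule stated |
| Injection before closure | Yes | Patient unconscious |
| Post-operative care | No | Assessors blinded; same analgesics |

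The third row is the unprotected interval. That randomisation precedes anaesthesia is an inference: a patient must be conscious to consent, randomisation follows consent, and fixation comes next. No clock time is given.

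**Step 2. The plan's own figure.** Inputs from the SAP are a difference of 1.5, SD 2.0, p-value .05 and power of 80% or higher. Two-sided testing and 1:1 allocation are assumed, since neither is stated. The normal formula is n = 2 × (1.96 + 0.842)² × 2.0² / 1.5² = 27.9, so 28 per group (29 by the t-test). The stated 40 is therefore not the minimum at 80%. It gives 91.2% power by the t-test, which meets the SAP's wording. The sample size neither supports nor refutes the present point.

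**Step 3. Dilution, by assumption.** Suppose a further fraction f of controls receive analgesia before the injection worth the full 1.5 points. The observed difference is 1.5 × (1 − f). Power is for the two-sided t-test with SD 2.0.

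| f | Difference | Underestimate | Power, 40 per group (stated minimum) | Power, 100 per group (planned) |
|---|---|---|---|---|
| 0 | 1.50 | 0% | 91.2% | 99.95% |
| 10% | 1.35 | 10% | 84.6% | 99.7% |
| 20% | 1.20 | 20% | 75.5% | 98.8% |
| 30% | 1.05 | 30% | 64.0% | 95.9% |

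**Step 4. False-positive direction, by assumption.** Suppose the injection has no effect, but use of some other analgesic measure before it is higher in the injection arm by 5 to 20 percentage points, and that measure lowers VAS by 1 to 2 points. Bias = imbalance × effect, which runs from 0.05 × 1 = 0.05 to 0.20 × 2 = 0.40 points, or 3 to 27% of 1.5. The standard error is 2.0 × √(2/n): 0.447 at 40 per group and 0.283 at 100. The normal approximation gives these two-sided type I error rates.

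| Bias (points) | 40 per group | 100 per group |
|---|---|---|
| 0.05 | 5.1% | 5.4% |
| 0.20 | 7.3% | 10.9% |
| 0.40 | 14.6% | 29.3% |

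The bias stays the same as n grows while the standard error shrinks, so a larger trial is more likely to declare a spurious difference.

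**The case against.** The strongest reply is that assignment is not disclosure. The research team randomises, and the documents do not say when, or whether, the surgeon or anaesthetist is told, nor who prepares the injection. Early randomisation that stayed concealed would create no difference in care. This stands, and it makes the care-related part of the point conditional. It does not remove that part, because no concealment is described and theatre staff are outside the stated blinding.

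Three stronger readings are tempting and are not supported.

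- *Regional blocks are being used, and used unequally.* The Protocol says "These injections may be equally effective at reducing pain compared to regional anesthesia with continuous infusions, and single-shot nerve blocks", which suggests that a block could substitute for the injection. But this is hedged feasibility background next to a statement about elective surgery. Neither document says that blocks are used in this trial.
- *Power falls below 80%.* This needs assumed extra analgesia in 20 to 30% of controls together with the minimum of 40 per group. At the planned 100 per group it does not occur.
- *Every patient whose operation is changed is lost.* VAS, patient-controlled analgesia use and time in hospital come from routine records, so a changed operation can still yield them. Only a patient with no operation clearly lacks post-operative outcomes. Since patients are blinded, loss that depends on the arm would have to come mainly from staff decisions.

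It is also fair to say that opening the assignment at closure is not a complete cure: the theatre team then knows the arm for the rest of the case. Concealing the assignment from the anaesthesia team would address much of the same risk without moving randomisation, though it would not prevent losses before surgery.

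**Conclusion.** The point holds as a cheap design improvement and not as a demonstrated bias. The documents support the sequence and the absence of protection in the interval. They do not support a statement that theatre staff know the arm or that care does differ, so the right wording is that it can.

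The 10 to 30% underestimate in Step 3 and the error rates in Step 4 show scale only. Every rate of extra analgesia and every worth attached to it is assumed, and the true size cannot be derived from the documents. The firm conclusions are that the direction could go either way and that enrolling 200 protects power but not the estimate. The loss of patients who are never operated on is the lesser part, and no rate is available for it.

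**What to change.** Keep consent where it is. Generate the allocation list in advance, and open the next sequentially numbered sealed assignment in theatre only when fixation is complete and closure is about to begin. Before opening it, record anaesthetic type, any regional block and intra-operative opioid. These are then true baseline variables, and patients who have no operation are never randomised. Record separately any analgesia given between opening and the end of the case.

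If early randomisation is kept, conceal the assignment from theatre staff until closure, report care before the injection and losses before surgery by arm, and define the analysis set as all randomised patients.

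The cost is Protocol wording, sealed assignments in theatre and a short record form. The practical burden is that the mixture, which contains morphine, must be prepared at short notice, or drawn up for every patient and discarded for controls.
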